4.4.5. Lost to Follow-up

A patient will be considered lost to follow-up if he/she repeatedly is unable to be contacted by the study site after hospital discharge.

The following actions must be taken if a patient repeatedly is unable to be contacted:

- The site must attempt to contact the patient and reschedule the missed visit as soon as possible, counsel the patient on the importance of maintaining the assigned visit schedule, and ascertain whether or not the patient wishes to and/or should continue in the study.

- In cases in which the patient is deemed lost to follow-up, the investigator or designee must make every effort to regain contact with the patient (where possible, 3 telephone calls and, if necessary, a certified letter to the patient's last known mailing address or local equivalent methods). These contact attempts should be documented in the patient's medical record.
- Should the patient continue to be unreachable, he/she will be considered to have withdrawn from the study with a primary reason of lost to follow-up.

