8. SAMPLE SIZE AND DATA ANALYSES

8.1. Determination of sample size

The decision to include 20 patients in the sentinel cohort was chosen arbitrarily.

The sample size for the expansion group has been determined to provide evidence of proof of concept efficacy should the treatment prove effective. The primary endpoint and futility rules are based on assessments at Day 14 to enable rapid decision making, and the assessment at Day 28 will also be presented as a secondary endpoint.

The detailed assumptions are as follows, and the calculations include the patients from the sentinel cohort that were treated with the same dose used for the expansion cohort:

Alpha	0.2 (one-sided)
Power	80%
Drop-Outs assumed	2%
Endpoint	Odds of patient alive and respiratory failure free by Day 14
Effect Size	78% Placebo 89% Antroquinonol
Futility boundary shape	Manually chosen. Odds Ratio of 3.5 at interim analysis 1 in favor of placebo, and 1.2 at interim analysis 2 in favor of placebo. Equivalent to 4 patients not in respiratory failure on antroquinonol vs 7 on placebo at interim analysis 1, or 26 patients not in respiratory failure on antroquinonol vs 28 on placebo at interim analysis 2. Nonbinding
Efficacy boundary shape	None

In addition, the performance of the study under the following scenarios for the efficacy of antroquinonol were also considered:

Antroquinonol harmful	78% Placebo 67% Antroquinonol
Antroquinonol no effect	78% Placebo 78% Antroquinonol

The nonbinding decision rules of the interim analysis and stopping probabilities under:

Look #	Sample Size	Futility Stopping Boundary Odds Ratio	Cumulative Futility Stopping Probability		
			Drug harmful	No effect	Drug effective
Interim analysis 1	20	3.5	25%	17%	5%
Interim analysis 2	80	1.2	79%	44%	9%
Final	174	0.697			

The decision rules may be modified pending discussion with the DMC, but any modifications will still be considered nonbinding; therefore, no adjustment for the final alpha will be made.

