## Statistical Analysis Plan

Sponsor Name: Golden Biotechnology Corporation

Sponsor Protocol ID: GH Covid-2-001

Covance Study ID: 000000203201

A total of 174 patients are planned to be randomized in a 1:1 ratio to antroquinonol or placebo.

The study will consist of a sentinel cohort of 20 patients (10 patients randomized to antroquinonol and 10 patients to placebo), and an expansion cohort of 154 patients (77 patients in each treatment group). Enrollment will pause after the 20th patient in the sentinel cohort has been enrolled and started treatment, until the results of the interim analysis 1 are known. Once the 20th patient in the sentinel cohort has completed 14 days of treatment, an unblinded Data Monitoring Committee (DMC) will assess the safety, tolerability, efficacy, and PK of 100 mg twice daily (BID) antroquinonol in COVID-19 patients in the sentinel cohort (interim analysis 1). The DMC will issue a recommendation to enroll patients for the expansion cohort, or to stop the study depending on the safety and futility assessment. Once the 80th patient has been enrolled, and completed 14 days of treatment, the DMC will review the safety, tolerability, and efficacy data (interim analysis 2). Enrollment may be restricted at the 100th patient until the DMC has completed the assessment to prevent excessive enrollment. The DMC will continue to review safety and assess the risk/benefit profile on an ongoing basis. A DMC Charter, which includes detailed processes, will be prepared.

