### 2.3 Sample Size

A total of 174 patients are planned to be randomized into the study:

- 20 patients in the sentinel cohort (10 patients in each treatment group)
- 154 patients in the expansion cohort (77 patients in each treatment group).

This enrollment level ensures 80% power to demonstrate proof of concept efficacy with one-sided alpha of 0.2.

The sample size is based on the following assumptions:

- The randomized allocation ratio is 1:1 between the antroquinonol group and the placebo group
- The proportion of patients alive and free of respiratory failure is approximately 78% on placebo vs 89% on antroquinonol

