## 6.2 Handling of Dropouts, Missing Data, and Outliers

Unless specified otherwise, no imputation for missing/partial dates will be performed for missing safety, efficacy, PK variables. For time-to-event efficacy variables, the censoring rules for no event data will be included in efficacy analysis section.

For patients with clinical improvement score above 2 or missing at discharge, missing scores on the next day after discharge will be imputed to 2. After above rule implemented, missing scores will be imputed using Last Observation Carried Forward for a maximum of 1 day at Day 7, 2 days at Day 14, and 4 days at Day 28.

Dates in original form will be used in all listings.

No rules for outlier detection are planned.

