#### 7.6.2 Secondary Efficacy Analysis

##### 7.6.2.1 Clinical Improvement Score as Measured by WHO COVID-19 Clinical Improvement Ordinal Scale

Clinical improvement measured as a score on the WHO COVID-19 Clinical Improvement Ordinal Scale will be analyzed using an ordinal logistic regression on Days 7, 14, and 28, with study treatment, clinical improvement score at baseline (as numerical variable), age at baseline ( $> 65$  years vs  $\leq 65$  years), and remdesivir or other authorized treatments for COVID-19 use at baseline (yes vs no) as covariates. The p-value for treatment effect will be provided based on the Wald test.

In addition, descriptive statistics will be provided for average score by treatment group, and the proportion of patients at or below each score, at each visit.

Time to 2-point improvement from baseline in WHO COVID-19 Clinical Improvement score, time to score of 2 or lower, and time to score of 0, will also be analyzed. The hazard ratio and its 95% confidence interval for these time-to-event endpoints will be estimated by Cox proportional hazard model, with treatment, remdesivir or other authorized treatments for COVID-19 use at baseline (yes vs no) and age at baseline ( $> 65$  years vs  $\leq 65$  years) as covariates. The analysis will be carried out using two different censoring rules: 1) Patients will be censored at the time they are provided any authorized treatment for COVID-19 not prescribed at baseline, or on Day 28 if they have not yet recovered or have died by Day 28; 2) Patients will only be censored on Day 28 if they have not yet recovered or have died by Day 28. The p-value for comparison between treatment groups will be obtained based on the Cox proportional hazards model described above. Median time to 2-point improvement, time to score of 2 or lower, and time to score of 0 will be estimated by Kaplan-Meier (KM) method, and the KM curve will be provided.

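### Apart from new-treatment censoring under rule 1, Day 28 is the only censoring time for the recovery endpoints, so living patients who leave without the event are carried as known not recovered to Day 28

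*SAP*

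**What the plan says.** SAP 6.2 makes no general provision for dropouts in time-to-event endpoints; it says that "the censoring rules for no event data will be included in efficacy analysis section". That section is SAP 7.6.2.1, which covers time to 2-point improvement, time to score 2 or lower, and time to score 0 on the WHO scale. It sets two rules:

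- Rule 1: "Patients will be censored at the time they are provided any authorized treatment for COVID-19 not prescribed at baseline", or else on Day 28 for patients not recovered or dead by then.
- Rule 2: "Patients will only be censored on Day 28 if they have not yet recovered or have died by Day 28".

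Protocol 8.4.2 likewise names only new antiviral therapy or Day 28, and says expressly that deaths count as not recovered by Day 28. SAP 7.6.2.3 uses Day 28 for virological clearance.

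Early exits are foreseen. Protocol 4.4.4 permits study withdrawal and 4.4.6 rules out replacement. Protocol 4.4.5 defines loss to follow-up as being unreachable after hospital discharge, and adds: "Should the patient continue to be unreachable, he/she will be considered to have withdrawn from the study". The table in Protocol 8.1 has a line "Drop-Outs assumed", set at 2%.

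SAP 6.2 also has a discharge rule. If the score at discharge is above 2 or missing, a missing score on the following day is set to 2. Any later carry-forward is limited to 1, 2 or 4 days at Days 7, 14 and 28.

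**The concern.** Censoring at time t tells the Cox and Kaplan-Meier analyses that the patient was watched up to t without the event. For a death, Day 28 is a stated and sensible convention. For a living patient last assessed on Day 6, it adds 28 − 6 = 22 days at risk in which recovery could not have been recorded.

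Three things follow on an affected endpoint. Kaplan-Meier recovery is understated. A real effect is pulled slightly toward a hazard ratio of 1 when losses are equal. When losses differ between arms, the hazard ratio is biased against the arm that loses more patients, even if the drug does nothing.

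**Working it through.** **1. Inputs from the documents.** "A total of 174 patients are planned to be randomized in a 1:1 ratio to antroquinonol or placebo" (SAP 2.2), so 87 per arm. Drop-outs 2% (Protocol 8.1). The censoring rules are as above. Neither document gives a recovery distribution, or a size or power for the recovery endpoints.

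**2. The plan's own figure.** The only stated figure concerns the primary endpoint: "This enrollment level ensures 80% power to demonstrate proof of concept efficacy with one-sided alpha of 0.2", assuming "The proportion of patients alive and free of respiratory failure is approximately 78% on placebo vs 89% on antroquinonol". For a fixed design, with pooled proportion 0.835:

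- SE under no effect = √(2 × 0.835 × 0.165 / 87) = 0.0563
- SE under the alternative = √((0.78 × 0.22 + 0.89 × 0.11) / 87) = 0.0557
- power = Φ((0.11 − 0.8416 × 0.0563) / 0.0557) = Φ(1.125) = 87.0%

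With both futility rules followed, 400,000 simulated trials give 79.5%, so the stated 80% reproduces. This point does not touch it.

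**3. Which endpoints are exposed.** This follows from the WHO scale and the SAP 6.2 discharge rule, read as applying to these endpoints.

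| Endpoint | Leaves in hospital, no event | Lost after discharge |
|---|---|---|
| Score 2 or lower | exposed | event already recorded or imputed |
| 2-point improvement from 4 (needs 2) | exposed | event already recorded or imputed |
| 2-point improvement from 3 (needs 1) | exposed | exposed if still at 2 |
| Score 0 | exposed | exposed |
| Virological clearance | exposed | exposed if no negative test yet |

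**4. Effect on Kaplan-Meier recovery.** Assume exponential recovery, a proportion p recovered by Day 28, and non-informative loss of a fraction d, uniform over follow-up. With no other censoring, the Day 28 rule estimates

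p − d × [p/Λ − (1 − p)], where Λ = −ln(1 − p).

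For p = 0.70, Λ = 1.204 and the bracket is 0.5814 − 0.30 = 0.2814.

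- d = 2%: 70 − 0.56 = 69.4%
- d = 10%: 70 − 2.81 = 67.2%
- d = 15%: 70 − 4.22 = 65.8%

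Simulation with daily times and 200,000 patients per arm gives 69.5%, 67.3% and 66.0%. Censoring at last contact gives about 70% throughout.

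**5. Effect on the hazard ratio (HR).** Two sets of assumptions, both with exponential recovery and non-informative loss:

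- *Spread loss:* loss over Days 1–27; 70% or 85% of placebo patients recovered by Day 28; true HR 1.0 or 1.4; 200,000 per arm.
- *Early loss:* loss over Days 2–14; placebo median 10 days; true HR 1.0 or 1.5; 87 per arm, 800 trials per scenario.

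| Loss, drug / placebo | Timing | HR, last contact | HR, Day 28 rule | Ratio |
|---|---|---|---|---|
| 2% / 2% | early | 1.50 | 1.49 | 0.99 |
| 2% / 2% | spread, 70% | 1.392 | 1.389 | 1.00 |
| 10% / 10% | early | 1.50 | 1.46 | 0.97 |
| 10% / 10% | spread, 70% | 1.381 | 1.368 | 0.99 |
| 10% / 2% | early | 1.51 | 1.36 | 0.90 |
| 10% / 2% | spread, 70% | 1.378 | 1.306 | 0.95 |
| 10% / 2%, no effect | spread, 70% | 0.991 | 0.946 | 0.95 |
| 10% / 2%, no effect | spread, 85% | 1.002 | 0.955 | 0.95 |
| 2% / 10%, no effect | spread, 70% | 0.999 | 1.045 | 1.05 |
| 2% / 10%, no effect | spread, 85% | 1.001 | 1.051 | 1.05 |
| 2% / 10%, no effect | early | 0.99 | 1.08 | 1.09 |

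With early loss of 10% on drug and 2% on placebo, the null HR under the Day 28 rule is about 0.93. With equal loss the null HR stays at 1.00. In patients, 10% against 2% is 0.10 × 87 = 8.7 against 0.02 × 87 = 1.7. These simulations apply every loss to one generic exposed endpoint; they do not model the discharge imputation.

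**The case against.** Four stronger readings are tempting, and the documents do not support them.

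- *Every unrecovered patient is censored on Day 28.* This is true of rule 2 only. Rule 1 censors earlier at a new authorized treatment.
- *All recovery endpoints suffer alike.* They do not. Loss to follow-up is by definition after discharge, and by then score 2 or lower, and 2-point improvement from baseline 4, already have their event. The hazard ratios above therefore do not describe those endpoints except for in-hospital withdrawals.
- *Diarrhea on active drug will create the imbalance.* Protocol 4.4.3 treats an adverse event as a reason to stop study drug and asks such patients to continue assessments to Day 28. Adverse event is not among the reasons for leaving the study in 4.4.4. It could act only indirectly, through patient withdrawal or a physician's decision. The documents support no 8-point difference in study exit.
- *Power collapses or false positives double.* Under early loss, simulated power fell from 70% to 47% with 10% lost on drug and 2% on placebo. With the reverse imbalance, one-sided 0.025 rejection was 6% under no effect. Both need five times the planned loss, in one arm only and all by Day 14.

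It can also be said that counting unknown status as not recovered is a chosen convention. SAP 7.6.2.2 does this explicitly for hospital stay when the discharge date is unknown. But SAP 7.6.2.1 makes no such statement for living leavers, whereas deaths are named. Nor is last-contact censoring free of assumptions: it requires withdrawal to be non-informative. That is a good reason to keep the present rule as a sensitivity analysis.

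What survives is that the rule as written gives the wrong follow-up time for living patients who leave without the event, and nothing else in the SAP corrects it.

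**Conclusion.** The point holds within limits. Apart from rule 1's new-treatment censoring, Day 28 is the only censoring time, so living patients who leave without the event are carried as known not recovered to Day 28. The exposure is mainly in-hospital withdrawals, 2-point improvement from baseline 3, time to score 0, and virological clearance.

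At the only documented loss rate, 2%, and balanced between arms, the hazard ratio moves by about 0.01 or less and Kaplan-Meier recovery falls by about half a percentage point. If one arm loses about 10% and the other 2%, which is an assumption, the hazard ratio on an exposed endpoint moves about 4 to 10% against the arm with more loss: a null value of about 0.93–0.96, or 1.05–1.09 the other way, depending on when the losses occur. Only secondary analyses are concerned. The change is worth making because it is cheap and the direction of the bias depends on an imbalance nobody can foresee.

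**What to change.** Put into SAP 7.6.2.1 and 7.6.2.3:

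> Living patients who withdraw or are lost before Day 28 without the event are censored at their last WHO-scale assessment (last PCR test for virological clearance), after the SAP 6.2 discharge imputation is applied. Patients known to have died, and patients followed to Day 28 without the event, are censored on Day 28.

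Leave rule 1's new-treatment censoring as it is, and keep the present Day 28 rule as a sensitivity analysis. Record the change in SAP section 8, which now declares no departure from the protocol, because Protocol 8.4.2 carries the same Day 28 rule. For clearance, also say what followed to Day 28 means: Protocol Appendix 5 schedules the Day 28 swab only for patients still in hospital.

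The cost is a short paragraph, one derived censoring date from data already collected, and one extra run of each affected model. The price in assumptions is non-informative withdrawal.

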**CONFIDENTIAL**

Document Date: 29 Nov 2021

Page 19 of 34

ST-AD-008 version 05

## Statistical Analysis Plan

Sponsor Name: Golden Biotechnology Corporation  
Sponsor Protocol ID: GH Covid-2-001

Covance Study ID: 000000203201

### 7.6.2.2 Duration of Hospitalization and ICU Stay

Duration in days of hospitalization and ICU stay up to Day 28 will be summarized descriptively and analyzed using normal regression, with treatment, remdesivir or other authorized treatments for COVID-19 use at baseline (yes vs no) and age at baseline ( $> 65$  years vs  $\leq 65$  years) as covariates. P-values for treatment effect will be provided using the Student's t-test.

Notes: 1) Only hospitalization or ICU stay days on or after the date of first dose of study treatment and up to Day 28 will be used in the calculation of duration of hospitalization or ICU stay, respectively; 2) Patients who have died or with unknown discharge date will be considered as continuing to require hospitalization or ICU stay up to Day 28.

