7.1.2. Secondary efficacy endpoints

7.1.2.1. *Clinical improvement*

The WHO COVID-19 Clinical Improvement Ordinal Scale will be used to assess a clinical improvement score on Days 7, 14, and 28. See [Appendix 7](#) for details on the scale.

7.1.2.2. *Duration of hospitalization*

The number of days a patient has been hospitalized prior to study entry will be recorded in the eCRF.

Duration of hospitalization is the total number of days the patient is hospitalized during their participation in the study, up to Day 28.

7.1.2.3. *Virological clearance*

PCR testing for SARS-CoV-2 will be performed at a local or central laboratory at screening. Results of a confirmatory COVID-19 test already done as SoC can be used to determine eligibility. All subsequent tests (Day 1 and later) will be performed by a central laboratory. The PCR testing for SARS-CoV-2 will be collected during hospitalization as noted in the Schedule of Assessments ([Appendix 5](#)) and evaluated by the central laboratory.

Virological clearance will be measured by:

- **Time to viral clearance:** This endpoint will measure the time (days) to the first negative test for COVID-19.
- **Rate of change in viral load:** if quantitative PCR results are performed, the level of virus will be measured over time (days).

7.1.2.4. *Vital status*

Patient mortality will be recorded up to Day 28 and summarized in the analysis on Days 7, 14, and 28. Every effort will be made to ascertain vital status in all randomized patients (eg, with a vital records search) up to Day 28.

7.1.2.5. *Duration of ICU stay*

Duration of ICU stay is defined as the total number of days the patient is managed in the ICU during their participation in the study, up to Day 28. The date of the start and stop of the ICU stay must be recorded in the eCRF; no daily assessment is needed.

7.1.2.6. *Respiratory failure free*

The proportion of patients alive and respiratory failure free will be evaluated on Days 7 and 28. Respiratory failure is defined as the need for invasive mechanical ventilation, non-invasive ventilation, high-flow oxygen, or ECMO. The date of the start of the respiratory intervention must be recorded in the eCRF; no daily assessment is needed.

7.1.2.7. *COVID-19 symptoms*

COVID-19 symptoms assessment at the times indicated in the Schedule of Assessments in [Appendix 5](#) will evaluate: presence or absence of dry cough, dyspnea (shortness of breath/

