8.4.2. Secondary efficacy outcome measures

Clinical improvement measured as a score on the WHO COVID-19 Clinical Improvement Ordinal Scale will be analyzed at each timepoint, adjusted for the clinical improvement score at baseline, age at baseline, and remdesivir or other authorized treatments for COVID-19 use at baseline, using an ordinal logistic regression on Days 7, 14, and 28. In addition, descriptive statistics will be provided for average score, and the proportion of patients at or below each score, at each timepoint. Time to 2-point improvement from baseline in WHO COVID-19 Clinical Improvement score, time to score of 2 or lower, and time to score of 0, will also be analyzed.

The hazard ratio and its 95% confidence interval for time to event outcomes will be estimated by Cox proportional hazard model, with patients censored at the time they are provided any antiviral therapy not prescribed at baseline, or on Day 28 if they have not yet recovered. Patients who die at any time will be considered not yet recovered by Day 28. Median time to 2-point improvement, time to score of 2 or lower, and time to score of 0 will be estimated by Kaplan-Meier (KM) method, and the KM curve will be provided. The p-value for comparison between groups will be obtained based on proportional hazards modeling stratified by the same covariates as the primary model.

Duration of hospitalization and ICU stay up to Day 28 will be analyzed using normal regression, using the same covariates as for the primary endpoint. Patients who die will be considered as continuing to require hospitalization or ICU stay up to Day 28 for the purposes of this analysis.

Time to virological clearance, measured as study days from start of treatment to first negative SARS-CoV-2 PCR test, will be evaluated using similar statistical methods as clinical

improvement. All patients who have died will be considered as not having cleared the virus by Day 28

Rate of change in viral load will be summarized descriptively and estimated using a Mixed Model for Repeated Measurements model. The model will include the treatment group, age, remdesivir or other authorized treatments for COVID-19 use at baseline, visit, and the interaction between visit and the treatment group as fixed factors, and will include the baseline value as a covariate. If a patient has tested negative, they are assumed to be negative until they are tested again.

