- h Efficacy parameter assessments: [1] Confirmation of whether the patient is discharged to home, is in the hospital, or has worsened to require an ICU. The number of days a patient has been hospitalized prior to study entry will be recorded in the eCRF. [2] PCR testing for SARS-CoV-2 will be performed by a local or central laboratory at screening. Results of confirmatory COVID-19 test already done as standard of care can be used to determine eligibility. All subsequent tests will be performed by a central laboratory at baseline/Day 1, Day 5 (+/-1 day) and Day 14 (+2 days). Also at Follow-up/EOS if patient is hospitalized. Either nasopharyngeal or mid-turbinate samples are allowed for central testing. Only one method should be used throughout the study for the participant. [3] Clinical improvement score will be measured using the WHO COVID-19 Clinical Improvement Ordinal Scale (refer to [Appendix 7](#)). [4] Patient mortality will be recorded up to Day 28. Every effort will be made to ascertain vital status in all randomized patients (eg, with a vital records search) up to Day 28. [5] Respiratory failure is considered as patient need for invasive mechanical ventilation, non-invasive ventilation, high-flow oxygen, or ECMO. The date of the start of the respiratory intervention must be recorded in the eCRF; no daily assessment is needed. [6] COVID-19 symptoms (presence or absence of dry cough, dyspnea (shortness of breath/ difficulty in breathing), or chills/rigors, myalgia (muscle pain), headache, sore throat, and loss of taste or smell; other symptoms that could be related to COVID-19) will also be assessed during hospitalization, on discharge, ET/EOT and Follow-up/EOS visit (at the site, home visit, or via telephone or telemedicine if patient has been discharged).

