## 8. Changes in Planned Analysis

No changes on statistical analysis methods from the protocol.

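### SAP 7.6.2.2 widens the protocol's deaths-only Day 28 rule to every unknown discharge date, without declaring it and without using the recorded patient setting

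*SAP*

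**What the plan says.** SAP 7.6.2.2 says that hospital and ICU days, counted from first dose to Day 28, are "summarized descriptively and analyzed using normal regression" on treatment, baseline use of authorized COVID-19 treatment and age group, with a t-test p-value. Its second note adds the imputation: "Patients who have died or with unknown discharge date will be considered as continuing to require hospitalization or ICU stay up to Day 28".

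Protocol 8.4.2 (and the synopsis) has a narrower rule: "Patients who die will be considered as continuing to require hospitalization or ICU stay up to Day 28 for the purposes of this analysis". It does not mention unknown discharge dates. SAP section 8 nevertheless reports "No changes on statistical analysis methods from the protocol".

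Three other places bear on the rule:
- Protocol 7.1.2.5 defines ICU stay as "the total number of days the patient is managed in the ICU" and adds that "The date of the start and stop of the ICU stay must be recorded in the eCRF".
- Protocol Appendix 5, footnote h, requires at visits: "Confirmation of whether the patient is discharged to home, is in the hospital, or has worsened to require an ICU". The schedule marks this at screening, Days 3, 5, 7 and 14, the discharge or early-termination visit, and Day 28.
- SAP 6.2 rules out imputing missing or partial dates unless stated otherwise, so a partly recorded discharge date may also be treated as unknown.

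**The concern.** A death carried to Day 28 is a deliberate penalty for a bad outcome. An unknown discharge date in a living patient is a recording gap, and the SAP gives it the same worst value. Nothing in the note limits this to patients last known to be in hospital, so data already collected can contradict the imputed value. The SAP can also contradict itself. A patient scored as ambulatory on Day 7 has reached the time-to-score-2-or-lower endpoint in 7.6.2.1, yet counts as hospitalized to Day 28 in 7.6.2.2.

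The ICU part has a similar gap. Read literally, a living patient never admitted to ICU could receive ICU days because a discharge date is missing.

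At stake are avoidable noise in two secondary endpoints, and bias if missing dates are unequal between arms. There is also a departure from the protocol that SAP section 8 does not record.

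**Working it through.** **Plan's own figure.** There is none. The documents give no SD, effect size or power for duration. The 80% power in SAP 2.3 is for the primary endpoint and is unaffected.

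**Error for one patient.** Take a patient recorded in hospital on Day 5 and as an outpatient on Day 7, with the discharge date missing. The true stay is 5 to 7 days and the rule gives 28. The overcount is 28 − 7 = 21 to 28 − 5 = 23 days. With 174/2 = 87 per arm, one such patient moves the arm mean by 21/87 = 0.24 days or more.

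**Effect on the test.** From the documents: 87 per arm; one-sided levels 0.025 and 0.2 (SAP 7.1); 2% dropout (Protocol 8.1), used as a proxy for unknown dates. Assumed: log-normal stays, median 7 days, log-SD 0.6, rounded up and capped at 28; 10% deaths per arm; stay 20% shorter on drug. Deaths and unknown dates are set to 28. A two-sample t-test stands in for the regression, without covariates. Simulated power at one-sided 0.025:
- no unknown dates: about 25%
- 2% per arm (0.02 × 87 = 1.7 patients): about 23%
- 5% per arm (0.05 × 87 = 4.4 patients): about 19%

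Other assumptions give a larger loss. With 85 per arm, median 6 days, log-SD 0.7, 5% deaths and a 25% shorter stay, power is 40%, 35%, 28% and 22% at 0%, 2%, 5% and 10% unknown.

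**Imbalance with no true effect.** Use median 7, log-SD 0.6, 5% deaths per arm, and unknown dates in 5% of placebo and 0% of drug patients.
- Mean of an uncapped stay: 7 × exp(0.6²/2) = 8.4 days. Rounding up adds about 0.5 and the cap removes about 0.1, giving 8.8.
- Arm mean with 5% at 28: 0.95 × 8.8 + 0.05 × 28 = 9.8 days.
- Shift on placebo: 0.05 × (28 − 9.8) = 0.91 days.
- Simulated SDs are about 7.5 (placebo) and 6.5 (drug), so SE = √[(7.5² + 6.5²)/87] = 1.06.
- Rejection rate: P(Z > 1.96 − 0.91/1.06) = P(Z > 1.10), about 13.5%. Simulation gives about 13%, against a nominal 2.5%. At the 0.2 level the rate is about 50%.

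With the imbalance reversed, the test is biased against the drug and rejects well below 2.5%. With balanced 28-day values the t-test keeps its level (0.024 to 0.027 at nominal 0.025).

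**ICU days, if the literal reading were programmed.** All ICU inputs are assumed. With no unknown dates and no treatment effect the mean is about 2.8 days. Giving 5% of all patients 28 days makes it 2.8 + 0.05 × (28 − 2.8) = 4.1. Limiting the rule to patients ever in ICU gives about 2.9.

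**Choice of test.** Power at one-sided 0.025, t-test against Wilcoxon, in the first model without unknown dates:
- 20% shorter stay, equal deaths (10%): 25% against 49%
- 20% shorter stay, 10% vs 5% at Day 28: 67% against 75%
- 10% shorter stay, 10% vs 5% at Day 28: 37% against 34%

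**The case against.** Unknown dates should be rare. Every patient starts in hospital, a discharge visit is scheduled, and Protocol 4.4.5 defines loss to follow-up as occurring after discharge. Bias also needs imbalance between arms, which is assumed here and which double-blinding makes less likely. These points stand and are why the effect is probably small. They do not justify overriding a recorded outpatient setting.

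A reader might infer that ICU days will certainly be miscoded. The documents do not support that. The first note in 7.6.2.2 treats hospital and ICU separately, the second speaks of continuing a stay, and a patient never in ICU has no ICU stay to continue. A programmer could reasonably score that patient 0. It is an ambiguity. Nor did the SAP bring ICU into the rule: the protocol's death rule already covers ICU stay.

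A reader might also infer that "analyzed using normal regression" costs a large amount of power and should give way to a rank test. No input in the documents fixes such a loss, and the comparison changes direction with how the drug acts. The trial is designed around preventing failure (78% vs 89% failure-free), which favours the mean-based test more than a pure effect on stay does. It is not even true that the rank test is weaker only under a pure mortality effect: the third comparison above contains both effects and the t-test is ahead. The SAP also already analyzes time to score 2 or lower, in effect time to leaving hospital, by Cox and Kaplan-Meier methods.

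Finally, the extension could be called data handling rather than a change of method. But it changes the endpoint value for living patients, so it belongs in section 8.

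**Conclusion.** The point holds as a defect in the imputation rule. The SAP widens a deaths-only rule without declaring it. As written, it assigns a wrong value to any living patient with a missing discharge date whose recorded setting shows an earlier return home. The ICU wording needs clarifying.

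The likely size is modest: a loss of about 2 points of power at 2% unknown dates per arm and 6 points at 5% in the main assumed model. A 5% vs 0% imbalance would raise the one-sided 0.025 error to about 13%. These figures rest on assumed stay distributions and death rates, on dropout as a proxy for unknown dates, and on a test without covariates. The endpoints are secondary with no stated power, and the primary analysis is untouched. The material does not support replacing normal regression.

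**What to change.** Amend SAP 7.6.2.2 as follows:
- Keep the Day 28 rule for deaths as in the protocol.
- For living patients with an unknown discharge date, end the hospital stay at the first later visit whose recorded setting is outpatient. Count to Day 28 only if the patient was last known in hospital.
- Apply the unknown-date rule for ICU only to patients with a recorded ICU admission who were last known in ICU. Give living patients never in ICU 0 ICU days.
- List the extension beyond the protocol in SAP section 8.

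Keep normal regression as the prespecified analysis. A van Elteren test stratified by the randomization factors, with deaths as worst rank, may be added as a sensitivity analysis.

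The cost is SAP wording and a little programming before unblinding. Setting and ICU dates are already collected. One limit remains: ending the stay at the first outpatient visit can still overstate it by up to the gap between visits (at most 14 days, between Days 14 and 28, if all visits are recorded).
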